9.3.3 Restrictions during the Study

The following concomitant medications will not be allowed while enrolled in the study:

Restricted medication	Examples (not comprehensive)	Wash out
Topical corticosteroids (on scalp or body), retinoids or anti-inflammatory agents (on scalp)	Topicort® (desoximetasone 0.25%) spray, Cortaid® (hydrocortisone 1%), Clobex® (clobetasol 0.05%), Diprolene® (betamethasone 0.05%), retinol, diclofenac, etc.	2 weeks
Topical anti-psoriatic medication (on scalp)	Psorcon® ointment/cream, Dovonex® (calcipotriene), Tazorec® (tazarotene), Vectical® (calcitriol), salicylic acid, anthralin, coal tar, etc., including medicated shampoos	2 weeks
Beta blockers, lithium preparations, anti-malarial agents or tanning booths	metoprolol, labetalol, Eskalith, Lithobid, quinine, etc.	2 weeks

CONFIDENTIAL PROTOCOL

An Open Label, Safety Study to Assess the Potential for Adrenal Suppression Following Maximal Use Treatment with Desoximetasone 0.25% shampoo(Taro Pharmaceuticals U.S.A., Inc.) in Patients with Scalp Psoriasis

Biologic treatment for psoriasis	Remicade® (infliximab), Enbrel® (etanercept), Humira® (adalimumab), etc.	12 weeks
Chemotherapy Radiation therapy		3 months
Systemic corticosteroids Systemic antipsoriatic treatment Systemic antibiotics PUVA therapy UVB therapy Prescription strength systemic anti-inflammatory agents	Prednisone (Short and occasional use of intranasal, inhaled or ophthalmic corticosteroids for acute and transitory conditions [e.g. allergic rhinitis] up to 1 mg per day is acceptable) methotrexate, cyclosporine, hydroxyurea *the use of acetylsalicylic acid for prophylactic use up to 325 mg/day is allowed, provided that the patient is on a stable dose for at least 3 months and the regimen will remain constant throughout the study	4 weeks
Systemic retinoids	Soriatane® (acitretin), Isotretinoin etc	4 weeks
Systemic immunosuppressive drugs	tacrolimus, pimecrolimus	8 weeks

Patients and will be advised to avoid environmental conditions that may exacerbate their disease state. Patients will be advised to avoid exposure to sunlight of a duration that would require application of sunscreen.

In addition, patients must have consistently used a single brand/type of hair care product (e.g., shampoo, conditioner, spray, etc.) for a minimum of 14 days prior to baseline. Patients will be asked to continue using the same brand/type and frequency of use throughout the study.

Patients will be questioned about all concomitant prescription and OTC medication use at each study visit. All concomitant medications will be recorded in the patient's study chart. Any patient who violates any of the listed restrictions should be dropped from continued participation in the study by the Investigator.

9.3.4 Removal of Patients from the Study

Patients will be advised that they are free to withdraw from the study at any time for any reason or, if necessary, the Investigator may withdraw a patient from the study to protect the health of that patient. A patient may also be withdrawn for not complying with study procedures. The clinical report will include all reasons for early withdrawals.

CONFIDENTIAL PROTOCOL

An Open Label, Safety Study to Assess the Potential for Adrenal Suppression Following Maximal Use Treatment with Desoximetasone 0.25% shampoo(Taro Pharmaceuticals U.S.A., Inc.) in Patients with Scalp Psoriasis

All patients who administer at least one dose of randomized study medication will be included in the safety analysis. If a patient terminates from the study early, all efforts will be made to complete their next visit study procedures. In case of early termination the Investigator shall fully document the reason for early termination. Reasons for early termination may include the following:

- Patient withdrew consent
- Significant adverse event that led the Investigator or patient to withdraw for safety reasons
- Worsening signs/symptoms of scalp psoriasis
- Development of an intercurrent condition or complication that could affect the safety of the patient or the validity of the evaluation of the patient's clinical state to an extent considered significant by the Investigator
- Signs and symptoms of possible HPA axis suppression
- Protocol deviations/violations that in the Investigator's opinion warrant discontinuation

Non-compliance with dosing need not be a reason for early termination. Patients who withdraw or are removed from the study will not be replaced. In the event a patient withdraws or is dropped from the study for any reason, the Investigator will request return of the unused product and report the reason for the discontinued participation.

When a patient discontinues early from the study, all study procedures required for the end of study should be performed at their last study visit. Patients who are discontinued from the study will be evaluated for safety and will be given, or referred for, appropriate treatment.

9.4 Treatments

9.4.1 Treatments Administration

The patient will be instructed to apply the study product to psoriasis-affected areas of the dry scalp once daily for 28 days. Patients are to move the hair away from the dry scalp so that one of the affected areas is exposed. A small amount of the study shampoo is to be applied directly to the affected area by gently squeezing the bottle. The shampoo is to be gently rubbed into the affected area. The same procedure is to be followed for other affected areas on the scalp. Patients will be instructed to use only enough to cover affected areas and avoid application to face, groin, armpits, lips or eyes. If during application the product comes in contact with the eyes or eyelids, patients will be instructed to rinse the area with abundant water immediately. Patients should not cover the head with a shower cap while the shampoo is on the scalp. The shampoo is to be left in place for 15 minutes before adding water, lathering and rinsing hair and scalp completely.

The patient will be instructed to apply the medication once daily until the patient's next scheduled visit. Each patient will be provided with a dosing diary in which they will be required to record dosing dates and times. These diaries should be brought to each visit so that the study staff may check compliance. At the end of the study, the dosing diaries will be retained in the patient's file as source documentation.

CONFIDENTIAL PROTOCOL

An Open Label, Safety Study to Assess the Potential for Adrenal Suppression Following Maximal Use Treatment with Desoximetasone 0.25% shampoo(Taro Pharmaceuticals U.S.A., Inc.) in Patients with Scalp Psoriasis

At Visit 1 qualified study patients will be provided with one 120 ml bottle of desoximetasone 0.25% shampoo along with instructions for dosing. This bottle should be weighed before dispensing and the weight recorded. At Visit 2, the bottle should be collected and weighed and a new 120 ml bottle of shampoo should be weighed and dispensed along with dosing instructions. This bottle will be returned and weighed at Visit 3.

Treatment compliance will be encouraged by instructing the patient on the proper dosing technique and by the use of the daily diary. Compliance will be assessed by evaluation of the diary.

9.4.2 Identity of Investigational Product

Desoximetasone 0.25% shampoo, w/w will be used in this study

9.4.3 Method of Assigning Patients to Treatment Groups

Patients will be assigned to the treatment in an open label fashion.

9.4.4 Packaging

This is an open-label study. The study product will contain a label with the following information:

- Protocol number
- Bottle number
- Space for patient number, patient's initials and dispensed date
- A note that the drug is for Investigational Use Only

9.4.5 Accountability

The Investigator or designee will maintain an inventory of all study product supplies received.

9.5 Study Conduct

The cortisol response test is to be done in the morning as the body's peak cortisol level is directly related to the event of awakening. Visit 1 and Visit 3 should be scheduled before noon and subjects should not apply the study drug within 12 hours of Visit 3.

9.5.1 Visit 1: Screening/Enrollment (Day 1), before 12 pm

1. **Informed Consent:** Patients who are willing to comply with study procedures will read and sign the informed consent form.
2. **Medical History and Demographics:** Review the patient's demographic and medical history including concomitant medication use within the last 12 weeks.
3. **Physical Examination:** A general physical exam will be conducted.
4. **HEENT Examination:** A general exam of the head, eyes, ears, nose and throat will be conducted at the clinic.
5. **% Scalp Affected:** Patient's scalp will be examined by Investigator/designated clinician to determine the percent surface area affected with plaque psoriasis. Refer to Appendix B.

CONFIDENTIAL PROTOCOL

An Open Label, Safety Study to Assess the Potential for Adrenal Suppression Following Maximal Use Treatment with Desoximetasone 0.25% shampoo(Taro Pharmaceuticals U.S.A., Inc.) in Patients with Scalp Psoriasis

6. **Vital Signs:** The patient's vital signs will be recorded (pulse, blood pressure, temperature and respiration rate).
7. **Pregnancy Test:** A pregnancy test will be required of all females of child bearing potential prior to enrollment.
8. **Investigator's Global Assessment:** Patient's scalp will be examined to determine a psoriasis severity score based on a global assessment of plaque elevation, scaling and erythema by the Investigator/designated clinician (refer to Appendix A). Patients with a score of 3 or more, indicating moderate to severe psoriasis will be included in the study.
9. **Concomitant Medication:** Review with the patient use of concomitant medication within the last 12 weeks.
10. **Confirm Inclusion/Exclusion Met:** Confirm the patient meets all inclusion/exclusion criteria.
11. **Laboratory Evaluations:** A blood sample will be collected for hematology and clinical chemistry testing. (See Appendix F).
12. **Cortisol Response Test:** All patients will have a cortisol response test performed according to the procedure detailed in Appendix D.
13. **Dispense Study Product:** If patient is eligible to enroll, record the weight of one bottle of study product and dispense with instructions.
14. **Provide Dosing Diary:** Provide diary and instruct patient regarding how it is to be filled out and how study product is to be used.
15. **Provide Patient Wristband:** Each patient will receive a wristband to indicate that the patient is using a medication that has the potential to cause HPA axis suppression.
16. Schedule Visit 2.

9.5.2 Visit 2 (Day 14 ± 2): Interim Visit

1. **Pregnancy Test:** A pregnancy test will be required of all females of child bearing potential prior to enrollment.
2. **Vital Signs:** The patient's vital signs will be recorded (pulse, blood pressure, temperature and respiration rate).
3. **HEENT Examination:** A general exam of the head, eyes, ears, nose and throat will be conducted at the clinic.
4. **% Scalp Affected:** Patient's scalp will be examined by Investigator/designated clinician to determine the percent surface area affected with plaque psoriasis. Refer to Appendix B
5. **Investigator's Global Assessment:** Patient's scalp will be examined to determine a psoriasis severity score based on a global assessment of plaque elevation, scaling and erythema by the Investigator/designated clinician (refer to Appendix A).
6. **Concomitant Medication:** Review with the patient use of new or change in ongoing concomitant medication since Visit 2.

CONFIDENTIAL PROTOCOL

An Open Label, Safety Study to Assess the Potential for Adrenal Suppression Following Maximal Use Treatment with Desoximetasone 0.25% shampoo(Taro Pharmaceuticals U.S.A., Inc.) in Patients with Scalp Psoriasis

7. **Adverse Events:** Patients will be questioned about any health status changes/adverse events since last visit. All events will be recorded.
8. **Ocular Assessments:** Patients will be questioned about any ocular discomfort as a part of safety assessments (refer to Appendix C)
9. **Evaluation of Patient Compliance to the Protocol:** Collect and review patient's dosing diary for compliance and provide a new diary. Non-compliance with dosing does not warrant dismissal from the study. Counsel non-compliant patients on dosing requirements of the study.
10. **Collect Study Product:** The used bottle of study drug will be collected and the weight recorded.
11. **Dispense Study Product:** If patient continues in the study, record weight of one bottle of study product and dispense.
12. **Provide Dosing Diary:** If patient continues in the study, provide a new dosing diary.
13. Schedule Visit 3

9.5.3 Visit 3 (Day 29 ± 2): End of Study or Early Termination, Before 12 pm

1. **Vital Signs:** The patient's vital signs will be recorded (pulse, blood pressure, temperature and respiration rate).
2. **Pregnancy Test:** A pregnancy test will be required of all females of child bearing potential.
3. **Physical Exam:** A general physical exam will be conducted.
4. **HEENT Examination:** A general exam of the head, eyes, ears, nose and throat will be conducted at the clinic
5. **% Scalp Affected:** Patient's scalp will be examined by Investigator/designated clinician to determine the percent surface area affected with plaque psoriasis. Refer to Appendix B
6. **Investigator's Global Assessment:** Patient's scalp will be examined to determine a psoriasis severity score based on a global assessment of plaque elevation, scaling and erythema by the Investigator/designated clinician (refer to Appendix A). Patients with a score of 3 or more, indicating moderate to severe psoriasis will be included in the study
7. **Concomitant Medication:** Review with the patient use of new or change in ongoing concomitant medication since Visit 2.
8. **Adverse Events:** Patients will be questioned about any health status changes/adverse events since last visit. All events will be recorded.
9. **Ocular Assessments:** Patients will be questioned about any ocular discomfort as a part of safety assessments (refer to Appendix C)
10. **Evaluation of Patient Compliance to the Protocol:** Collect and review patient's dosing diary for compliance.
11. **Collect Study Product:** The used bottle of study product will be collected and the weight recorded.

CONFIDENTIAL PROTOCOL

An Open Label, Safety Study to Assess the Potential for Adrenal Suppression Following Maximal Use Treatment with Desoximetasone 0.25% shampoo(Taro Pharmaceuticals U.S.A., Inc.) in Patients with Scalp Psoriasis

12. **Laboratory Evaluations:** A blood sample will be collected for hematology and clinical chemistry testing. (See Appendix F).
13. **Cortisol Response Test:** All patients will have a cortisol response test performed according to the procedure detailed in Appendix D.

9.5.4 Visit 4 (Day 42 ± 4): Follow-up Phone Call

A phone call will be conducted approximately 14 days after the subject has completed dosing to follow-up on any new adverse events that may have occurred.

9.6 Study Procedures

9.6.1 Informed Consent

No patient will be entered into the study without reading, understanding, and signing an informed consent. If any other language is required, translation will be performed by a certified translator.

9.6.2 Demographics

At screening, each patient shall be required to provide basic demographic information: date of birth, gender, ethnicity and race.

9.6.3 Medical History

At Visit 1, patients will be questioned about medical history, including acute and chronic medical history and medical history relevant to their scalp psoriasis, as well as all medication use within the past 12 weeks.

9.6.4 Vital Signs

The patient's vital signs will be recorded (heart rate, blood pressure, temperature and respiration rate) at Visit 1, 2, and 3.

9.6.5 Physical Exam

A general physical exam will be conducted at Visit 1 and Visit 3. The physical exam must include a dermatological examination as a minimum.

9.6.6 HEENT Exam

A head, eye, ear, nose, throat (HEENT) examinations will be conducted at each clinic visit.

9.6.7 Percent Scalp Affected

Patient's scalp will be examined by Investigator/ designated clinician to determine the percent surface area affected with plaque psoriasis at all visits. At each subsequent visit, the % affected area will be monitored and documented. Refer to Appendix B.¹⁶

9.6.8 Investigator Global Assessment

Patient will be examined to determine the severity of scalp psoriasis based on a global assessment of plaque elevation, scaling and erythema by the Investigator/designated clinician (refer to Appendix A).

CONFIDENTIAL PROTOCOL

An Open Label, Safety Study to Assess the Potential for Adrenal Suppression Following Maximal Use Treatment with Desoximetasone 0.25% shampoo(Taro Pharmaceuticals U.S.A., Inc.) in Patients with Scalp Psoriasis

9.6.9 Ocular Discomfort Assessment

Ocular discomfort will be assessed by subjects and reported to clinic staff during scheduled visits (refer to Appendix D). If the shampoo comes into contact with the patient's eyes, the patient will be asked to report the contact at each visit.

Ocular safety evaluations will be assessed at the discretion of the Investigator based on the findings of the HEENT exam performed at each visit along with the ocular discomfort reported by the patient. Medical records associated with the ocular safety evaluation should be obtained for the study chart.

9.6.10 Concomitant Medication Use

At Visits 1-3 and during the telephone follow-up phone call (Visit 4) patients will be questioned about current and concomitant medication use over the previous 12 weeks. At all Interim Visits patients will be questioned about ongoing or new concomitant medication use.

9.6.11 Pregnancy Test

Urine pregnancy tests on females of child-bearing potential will be performed at Visit 1, 2 and 3. The test must be negative for the patient to be eligible for inclusion in the study. If the patient is of non-childbearing potential, the source document must list the reason why she is of non-childbearing potential (e.g., postmenopausal).

Any patient who becomes pregnant during the study must be discontinued and End of Study procedures completed. The outcome of the pregnancy will be followed by the Investigator to birth or early termination as appropriate. The pregnancy will be reported as an AE.

9.6.12 Dispensing Study Product

At Visit 1 patients that satisfy all of the inclusion/exclusion criteria will be dispensed one bottle of the study product and dosing instructions. At Visit 2 (Day 14) a new bottle of study product will be dispensed.

The weight of the study product should be recorded before dispensing.

9.6.13 Collecting Study Product

Study product bottles will be collected and weighed at Visits 2 and 3.

9.6.14 Dosing Instructions and Diary

Patients will be provided with a diary to record the time and date of dosing, other concomitant medications and adverse events. Patients applying fewer than 75% or more than 125% of the required doses will be considered non-compliant with dosing. Compliance with dosing will be verified by the use of the patient diaries.

9.6.15 Dosing Compliance

Dosing compliance will be checked by site staff at Visits 2 and 3. Patients taking fewer than 75% or more than 125% of the scheduled doses will be considered non-compliant with dosing. Compliance with dosing will be verified by the use of the patient diaries.

CONFIDENTIAL PROTOCOL

An Open Label, Safety Study to Assess the Potential for Adrenal Suppression Following Maximal Use Treatment with Desoximetasone 0.25% shampoo(Taro Pharmaceuticals U.S.A., Inc.) in Patients with Scalp Psoriasis

Compliance Criteria			
Duration	Scheduled Doses	Not more than 125% (doses)	Not less than 75% (doses)
28 Days	28	35	21

9.6.16 Patient Wristband

Each patient who enters the study will be provided with a wristband at Visit 1 to identify that the patient is taking a medication that could potentially cause HPA axis suppression. The patient should be instructed to wear the wristband for the duration of the study.

9.6.17 Laboratory Evaluation

At Visit 1 and Visit 3 a blood sample will be collected for hematology and clinical chemistry testing (See Appendix F).

9.6.18 Cortisol Response Test

At Visit 1 and Visit 3 all patients will have a cortisol response test performed according to the procedure detailed in Appendix D. The resulting blood sample should be sent to ACM Global Laboratory for immediate testing.

The test at the End of Study visit should not be performed if the patient dosed within 12 hours.

A patient will be considered to have normal basal cortisol level and adrenal function if they meet all three criteria listed below under Normal. Failure to meet any of these criteria is indicative of abnormal adrenal function or potential HPA axis suppression, even in absence of related symptoms (e.g. nausea, headache, myalgia, fatigue or loose stool); for abnormal results, the patient will be monitored in accordance to the follow-up schedule below.

	Cortisol Results	
	Normal	Abnormal
Basal (pre Cortrosyn™ injection)	≥ 5 mcg/100ml	< 5 mcg/100ml
30 minutes post Cortrosyn™ injection	≥ basal value + 7	< basal value + 7
	> 18 mcg/100ml	≤ 18 mcg/100ml

HPA Axis suppression will be defined as a 30 minute post Cortrosyn™ injection level cortisol level of ≤ 18 mcg/100ml. If the Visit 1 Cortisol Response Test shows signs of HPA axis suppression as defined above the patient will be contacted and instructed to discontinue the use of study product, not to initiate any new steroid therapy, topical or otherwise and an End of Study Visit will be scheduled to conduct a Cortisol Response Test at least 28 days after the initial Cortisol Response Test at Visit 1 to assess for HPA axis suppression. At Visit 3 the study treatment period will be over, any patients with results of HPA axis suppression will be advised not to initiate any new steroid therapy, topical or otherwise, and to return to the site in 28 days at which time they will be assessed for HPA axis suppression.

CONFIDENTIAL PROTOCOL

An Open Label, Safety Study to Assess the Potential for Adrenal Suppression Following Maximal Use Treatment with Desoximetasone 0.25% shampoo(Taro Pharmaceuticals U.S.A., Inc.) in Patients with Scalp Psoriasis

Any patient presenting with symptoms of HPA axis suppression, such as nausea, headache, myalgia, fatigue or loose stool, will be referred to an endocrinologist. As an additional safety precaution, wristbands identifying the patient as someone suffering from adrenal suppression secondary to steroid withdrawal will be provided to alert medical personnel should any emergencies arise before adrenal function returns to normal.

If the results of the cortisol response test still show signs of HPA axis suppression 28 days after discontinuing therapy the patient will be asked to return in 28 days (56 days after discontinuing steroid therapy) for another follow-up test. If the patient is still showing signs of HPA axis suppression 56 days after discontinuing steroid therapy and presents with related symptoms, the patient will be referred to an endocrinologist.

If HPA axis suppression persists for 56 days after discontinuing steroid therapy, but the patient has no symptoms they will be asked to return in 28 days (84 days after discontinuing steroid therapy) for another follow-up test. If HPA axis suppression persists for 84 days after discontinuing steroid therapy the patient will be referred to an endocrinologist regardless of symptoms.

Patients should not be subjected to Cortrosyn™ testing, or any other challenge to their adrenal response, any sooner than 4 weeks from their last Cortrosyn™ test.

Follow-Up Schedule for Patients showing signs of HPA Axis Suppression

Days after d/c	HPA Results	Symptoms	Patient Course
28	Normal	N/A	Study over
28	Abnormal	Yes	Refer to endocrinologist
28	Abnormal	No	Repeat test in 28 days
56	Normal	N/A	Study over
56	Abnormal	Yes	Refer to endocrinologist
56	Abnormal	No	Repeat test in 28 days
84	Normal	N/A	Study over
84	Abnormal	Yes or No	Refer to an endocrinologist

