4.0 SYNOPSIS

Protocol Number	DSXS 1538a
Title	An Open-Label, Safety Study to Assess the Potential for Adrenal Suppression Following Maximal Use Treatment with Desoximetasone 0.25% Shampoo (Taro Pharmaceuticals U.S.A., Inc.) in Patients with Moderate to Severe Scalp Psoriasis
Objectives	
The objectives of this study are to:
 
1. Evaluate the potential of desoximetasone 0.25% shampoo to suppress HPA axis function in patients with moderate to severe scalp psoriasis.2. Evaluate the efficacy parameters and adverse event (AE) profiles of desoximetasone 0.25% shampoo administered to patients with moderate to severe scalp psoriasis.
Sponsor	Taro Pharmaceuticals U.S.A., Inc.
Name of Test Product	Desoximetasone 0.25% shampoo
Route of Administration	Topical
Study Design	An open-label, safety study to assess the potential for adrenal suppression following maximal use treatment with desoximetasone 0.25% shampoo applied once-daily for 28 days in adult patients with moderate to severe scalp psoriasis. Each patient is expected to receive 28 doses of study product.
Study Population	Up to 40 patients will be enrolled to obtain 20 evaluable male or female patients 18 years of age or older with a confirmed diagnosis of moderate to severe plaque psoriasis of the scalp with $\geq 25\%$ scalp affected.
Study Conduct	All patients will attend the clinic for 3 scheduled visits and a telephone follow-up phone call (Visit 4): Visit 1: Screening /Enrollment (Day 1) Visit 2: Interim Visit (Day 14 ± 2) Visit 3: End of Study (Day 29 ± 2) or Early Termination Visit 4: Follow Up (Day 42 ± 4) Telephone Phone Call If 10 or more patients experience biochemical abnormal values suggestive of possible HPA axis suppression, enrollment will be stopped. Such abnormality is defined by a 30 minute post Cortrosyn™ injection level cortisol level of ≤ 18 mcg/100ml during the Cortisol Response Test.
Inclusion Criteria	
1. Male or non-pregnant, non-lactating females 18 years of age or older.2. If female and of childbearing potential, prepared to abstain from sexual

CONFIDENTIAL PROTOCOL

An Open Label, Safety Study to Assess the Potential for Adrenal Suppression Following Maximal Use Treatment with Desoximetasone 0.25% shampoo(Taro Pharmaceuticals U.S.A., Inc.) in Patients with Scalp Psoriasis

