#### **5. STUDY ENDPOINTS AND ANALYSIS POPULATIONS**

##### **Primary Outcome Measures:**

Hypothalamic Pituitary Adrenal (HPA) Axis Response to Cosyntropin demonstrating the absence or presence of adrenal suppression at the end of treatment defined by the following criteria: 30 minute post Cortrosyn™ injection level cortisol level of  $\leq 18$  mcg/100ml during the Cortisol Response Test.

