## **6.2 Statistical Analyses**

### **6.2.1 Safety Analysis of Potential HPA Axis Suppression**

Dosing will be once daily for 28 days. Patients who have normal adrenal function at baseline, use at least 21 doses of the study product and have data from a post-treatment cortisol response test will be included in the analysis.

The primary analysis of interest is to assess the proportion of patients considered to have demonstrated possible HPA axis suppression following treatment with the study medication.

A logistic regression of the proportion of patients in the study with HPA axis suppression may be performed as exploratory analysis with % scalp affected as a covariate. This will depend on the distribution of the % scalp data collected. See Appendix D for results from the cortisol response test considered indicative of potential HPA axis suppression.

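### The Visit 3 window (Day 29 ± 2) permits a cortisol test 1 or 2 days inside the protocol's own 4-week minimum, and the primary HPA set has no upper limit on time since last dose (minor)

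*Protocol*

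**What the plan says.** Protocol 9.6.18 requires a cortisol response test at Visit 1 and Visit 3 for every patient. It says patients should not have Cortrosyn testing, or "any other challenge to their adrenal response, any sooner than 4 weeks from their last" such test. Appendix D of the protocol and Appendix D of the SAP repeat this.

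Visit 1 is Day 1. Protocol 9.5.3 is headed "Visit 3 (Day 29 ± 2): End of Study or Early Termination". Section 9.6.18 adds: "At Visit 3 the study treatment period will be over". The synopsis states the planned exposure: "Each patient is expected to receive 28 doses of study product".

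For patients who already show suppression at Visit 1, section 9.6.18 asks the site to "conduct a Cortisol Response Test at least 28 days after the initial Cortisol Response Test at Visit 1". For early terminators, section 9.3.4 says that "all study procedures required for the end of study should be performed at their last study visit".

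SAP 5 defines the primary outcome as the response to cosyntropin "demonstrating the absence or presence of adrenal suppression at the end of treatment". Under SAP 6.2.1, those with a normal baseline test who "use at least 21 doses of the study product and have data from a post-treatment cortisol response test will be included in the analysis". Protocol 10.1.2 sets the same three conditions. The only timing rule on the test itself is a lower limit: no dose within the preceding 12 hours (9.5, 9.6.18).

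**The concern.** The visit window and the minimum interval between tests were set separately and do not agree at the early edge. A site that books Visit 3 on Day 27 or 28 keeps to the schedule but goes against the interval rule. It also ends treatment before the planned 28 doses, in a study meant to measure suppression at maximal use. Such a visit is in window, so the out-of-window rows of the deviation table (T16.1.9.2) would not pick it up.

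The second issue concerns what the primary proportion measures. Protocol 7.3 says adrenal function tends to recover quickly once the steroid is withdrawn. If some patients in the primary set have been off drug for a week or more, any recovery before the test turns a suppressed patient into a normal one. That lowers the reported proportion, which is the unsafe direction for a safety study. With 20 evaluable patients, each reclassified patient moves the result by 5 percentage points.

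**Working it through.** **Inputs.** First test on Day 1; Visit 3 on Days 27 to 31; minimum interval 4 weeks = 28 days; 28 once-daily doses planned; at least 21 doses for the primary set; 20 evaluable patients.

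**Assumptions.** The first dose is on Day 1 and one dose is taken per day. No dose is taken on the day of Visit 3, which follows from a visit before noon and the 12-hour rule.

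**Plan's own figure.** The compliance limits in protocol 9.6.15 reproduce: 0.75 × 28 = 21 and 1.25 × 28 = 35. A patient with 21 doses has 21/28 = 75.0%, which is not below the limit, so that patient is compliant.

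**Day arithmetic.** Interval = visit day − 1. Maximum doses = the smaller of 28 and visit day − 1. Days off drug = visit day − day of last dose.

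| Visit 3 day | Days since Day 1 test | Meets 28-day minimum | Maximum doses | Days off drug, full dosing | Days off drug, last dose Day 21 |
|---|---|---|---|---|---|
| 27 | 26 | no | 26 | 1 | 6 |
| 28 | 27 | no | 27 | 1 | 7 |
| 29 | 28 | yes | 28 | 1 | 8 |
| 30 | 29 | yes | 28 | 2 | 9 |
| 31 | 30 | yes | 28 | 3 | 10 |

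Two of the five permitted days fall short of 28 days. Exposure on those days is at most 26/28 = 92.9% or 27/28 = 96.4% of plan.

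**Can the Day 21 stopper reach the primary set?** Yes. The dose count is met. Section 9.3.4 does not require withdrawal for missed doses. Neither protocol 10.1.2 nor SAP 6.2.1 mentions time since last dose.

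**What one patient is worth.** 1/20 = 5 points. The planned table T16.1.9.4 gives no interval; the exact (Clopper-Pearson) 95% intervals below were calculated for this note.

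- 3/20 = 15.0% (3.2 to 37.9)
- 2/20 = 10.0% (1.2 to 31.7)

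**What the planned outputs show.** L16.2.5.1 lists the date of last dose and L16.2.6.1 lists the date of the test. Days off drug can be obtained by joining them, but no planned output gives that number or relates it to the primary result.

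**The case against.** **The window permits an early test but does not require one.** This stands. A reader might infer that a site cannot follow both rules. It can: Days 29, 30 and 31, including the nominal day, satisfy both. The interval rule is worded as advice and sits beside the follow-up schedule for suppressed patients. It nevertheless speaks of patients in general, and 9.6.18 itself counts 28 days from the Visit 1 test for those suppressed at baseline, so that test does start the clock. Nothing in the documents suggests that 26 rather than 28 days changes the test result, and 26 or 27 doses is well above the 75% floor.

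**The same rule might seem to call for delaying early terminators' cortisol test until Day 29.** The documents do not say which rule has priority for these patients, and delay has real costs. For a last dose on Day 21 to 27, a test the next day is 1 day off drug; waiting until Day 29 makes it 29 − 21 = 8 down to 29 − 27 = 2 days. Suspected suppression is a listed reason for termination, so the delay would fall on patients who need the test soonest. Discontinued patients may also start other treatment, and the advice against new steroids is given only to those whose test shows suppression. Testing at the last visit is closer to end-of-treatment status.

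**The 24-hour row in T16.1.9.2 might look like a misstatement of the 12-hour rule.** The two do different jobs. The 12-hour rule guards against dosing too recently. The row counts patients whose last dose was not about a day before the visit, so it would flag the Day 21 stopper. It should stay. It does not give the number of days or feed into T16.1.9.4.

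**The size of any bias is not documented.** This stands. The only recovery time reported is normal function 28 days after treatment in the three suppressed patients of the spray study (7.3). One can assume a 3/21 on-drug rate from that twice-daily product, k = 1 to 4 late-tested patients and a recovering fraction r of 25 to 100%. The expected shortfall is then k × (3/21) × r / 20, or 0.2 to 2.9 points. None of these inputs is established for the shampoo, so the range is an illustration and not an estimate. The scenario also needs a patient who stops entirely, despite dosing counselling for non-compliant patients at Visit 2, and still attends.

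**Conclusion.** The first part is wrong as written, but small: 2 of 5 in-window days put the test 26 or 27 days after the first, against the protocol's 28, and hold exposure to 92.9% or 96.4% of plan. This rests only on both tests being done on the stated days; the dose counts also assume dosing from Day 1.

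The second part is an unset limit, not an error. Time off drug in the primary set can reach 6 to 10 days for a patient who stops on Day 21, against at most 3 for a full-dose completer seen in window. The direction of any effect is known (downward); its size is not, and a claim that the primary proportion is materially biased would go beyond the documents.

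Overall severity is minor.

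**What to change.** **Visit 3 window.** Change it to Day 29 to 31 (Day 29 +2/−0) wherever it appears. Test intervals become 28 to 30 days and a full 28 doses is always possible. The cost is a 3-day window instead of 5, and the Day 21 stopper's time off drug becomes 8 to 10 days instead of 6 to 10. If enrolment has ended, list any Day 27 or 28 test as a deviation from the 4-week rule.

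**Time off drug.** Keep the primary set and the 28-dose regimen. Derive days from last dose to test from the dates in L16.2.5.1 and L16.2.6.1, and show them in L16.2.6.1. Add one sensitivity row to T16.1.9.4 for patients tested within 3 days of the last dose. The 3-day cut is the most a full-dose completer can reach in window; it is not based on recovery data. No new data are needed. The cost is fewer patients in that row: for example, 0/17 has an upper exact 95% limit of 19.5%, against 16.8% for 0/20.

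**No change** to the timing of early terminators' cortisol test or to the 24-hour deviation row.
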